#### 6.1.3.1 Model checking procedures

Model checking will not be performed in this exploratory study.

#### 6.1.3.2 Graphical presentation of results

For Cohort A, model estimated means of the treatment at each timepoint will be provided along with their 80% CI.

#### Commercially Confidential Information

For Cohort B, individual summary plots by treatment for each group of C3 deposit score (activity, chronicity and mesangial) as well as for the total C3 Deposit Score will be provided.

#### 6.1.3.3 Sensitivity analyses

Commercially Confidential Information

#### 6.2 Secondary objectives

#### 6.2.1 Variables

The secondary variables supporting the secondary objectives are provided below for all cohorts:

- Renal parameters:
  - Raw and ratio to baseline in UA, UACR, UP and UPCR (all from 24h urine collection)
  - Raw and ratio to baseline in creatinine clearance (from 24h urine collection)
  - Raw and change from baseline in serum creatinine and eGFR
  - Hematuria (from 24-h urine collection)
  - Using the DuBois and DuBois equation, the creatinine clearance is defined as follows:

$$CrCl = \frac{U_{Cr} \times U_{Vol}}{P_{Cr} \times T_{min}} \quad in \ mL/min$$

where,

- $U_{cr}$  is urine creatinine in mg/dL from Q2
- $\circ$   $U_{Vol}$  is urine volume of the 24h urine in mL (from eCRF) and Q2
- $\circ$  *PCr* is plasma creatinine in mg/dL from Q2
- $\circ$  Tmin is the time of collection in minutes, so for example, 1440 min for 24
- Using the Chronic Kidney Disease Epidemiology Collaboration (CKD-EPI) equation, the eGFR is calculated as follows:

 $GFR = 141 \times \min(S_{cr}/\kappa, 1)^{\alpha} \times \max(S_{cr}/\kappa, 1)^{-1.209} \times 0.993^{Age} \times 1.018[\text{if female}] \times 1.159[\text{if black}]$ 

where,  $S_{cr}$  is serum creatinine,  $\kappa$  is 0.7 for females and 0.9 for males,  $\alpha$  is -0.329 for females and -0.411 for males, min indicates the minimum of  $S_{cr}/\kappa$  or 1, and max indicates the maximum of  $S_{cr}/\kappa$  or 1. The equation does not require weight because the results are reported normalized to 1.73 m2 body surface area, which is an accepted average adult surface area.

- Ratio to baseline of UPCR and UACR derived from 24-h urine collection (only for Cohort B)
- Raw plasma levels of Bb from BMD and serum C3 from central lab, and their ratio to baseline.

Baseline for:

- all 24-h urine collection parameters, is defined to be the 24-h urine collection on Day 1 to Day 1.
- serum creatinine and eGFR, is defined to be the last available assessment prior to the first dose of study drug.
- plasma levels of Bb from BMD and serum C3 from central lab is defined to be the baseline visit assessment.

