1.2 Purpose

The purpose of this study is to assess the clinical efficacy, pharmacodynamics, safety, tolerability and pharmacokinetics of LNP023 in patients with C3 glomerulopathy (C3G) and to evaluate the effect of different doses of LNP023 on complement biomarkers CCI

. C3G patients who have not received a kidney transplant and have reduced C3 blood levels will be included in Cohort A, C3G patients who have received a kidney transplant and have C3G recurrence will be included in Cohort B.

2 Objectives and endpoints

Table 2-1 Objectives and related endpoints

Objective(s)		Er	Endpoint(s)	
Primary objective(s)		Er	Endpoint(s) for primary objective(s)	
•	Cohort A: To evaluate the efficacy of LNP023 in reducing proteinuria at Week 12	•	Ratio to baseline of Urine Protein to Creatinine concentration Ratio (UPCR) derived from 24h urine collection.	
•	Cohort B: To assess histopathological changes in kidney biopsies at Week 12	•	Change from baseline in C3 Deposit Score (based on immunofluorescence microscopy).	
Se	Secondary objective(s)		Endpoint(s) for secondary objective(s)	
•	All Cohorts: To assess the relationship between LNP023 dose and pharmacodynamic biomarkers	•	Biomarker levels of blood Bb	
•	All Cohorts: To assess the relationship between LNP023 dose and proteinuria	•	24h urine UPCR and UACR.	
•	All Cohorts: To assess the effect of LNP023 on renal function	•	(i) change in and (ii) evolution of: urinary albumin (UA), urinary protein (UP) excretion; urine albumin to creatinine ratio (UACR) urine protein to creatinine ratio (UPCR), serum creatinine, estimated glomerular filtration rate (eGFR, using CKD-EPI formula), creatinine clearance, hematuria	
•	All Cohorts: To assess the effect of LNP023 on alternative complement pathway hyperactivity	•	Blood level of C3.	
•	All Cohorts: To assess the safety and tolerability of LNP023	•	ECG parameters, vital signs, safety laboratory assessments CCI , AEs and SAEs.	
•	All Cohorts: To assess the plasma and urine pharmacokinetics of LNP023 in patients with C3G	•	Plasma: Non-compartmental parameter analysis related to total drug, including but not limited to Cmax, Tmax, AUClast, AUCtau and Ctrough (Cmin) after the first dose on Day 7, Day 14, Day 21 and Day 28, as well as Cmin on Days 92, and 99 or 176 and 183.	
		•	Urine: Non-compartmental parameters, including but not limited to total cumulative urinary excretion (Ue) and renal plasma clearance (CLr).	

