4.1 Rationale for study design

The study has two separate cohorts (A and B), since two distinct C3G patient populations are investigated.

In both Cohorts the study treatment period starts with a within-patient dose-escalation portion of 4 weeks, to establish a Dose-PD and PK-PD relationship for LNP023 and to assess the relationship between LNP023 PD-effect and efficacy. To this end patients will be treated with increasing doses of LNP023,

Commercially Confidential Information

A PK assessment will be done on the last day of the respective dose level. The key biomarkers that will be assessed in this study are C3, and Bb as they have been shown to be dysregulated in patients with C3G (Nester and Smith 2016; Zhang et al 2014). Other biomarkers may be investigated.

Treatment period following the dose-escalation portion, includes a CCI period for both Cohorts. In Cohort A, this will be used to assess the primary objective of efficacy with LNP023 (200 mg dose CCI), i.e., to reduce proteinuria in the specific C3G non-transplanted population. This endpoint was chosen since urinary protein levels are known to correlate with kidney function/inflammation and therefore are expected to provide an objective means to measure drug effect. Importantly, Cohort B will also assess histopathologic improvement in renal biopsies. Biopsy response will be investigated in transplanted patients, due to higher availability of preexisting baseline biopsies (biopsies taken within 3 months before the baseline visit) and the higher acceptance of kidney biopsies at the end of treatment in this particular population.

Commercially Confidential Information

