Hematology ^{7,11}	Х			Χ		Х	Х			Х			Χ			Х		Χ	Χ	Χ
Blood chemistry ^{7,11,12}	Х			Χ		Х	Х			Х			Χ			Х		Χ	Χ	Χ
Urinalysis ^{7,11}	Х			Χ		Х	Х			Х			Χ			Х		Χ	Χ	Χ
Vaccination ^{13,14}		Х	X ¹⁵																	
Study drug dispensation						Х			X ²⁷			X ²⁷			X ²⁷			X	Х	
24-hours urine collection ¹⁶		X ³¹				Х										Х				Х
Spot urine collection - First Morning Void ⁷		X ¹⁷		X ¹⁷			X ¹⁷			X ¹⁷			X ¹⁷					X ¹⁷	X ¹⁷	
Spot urine collection - Mid Stream ^{18,19}						Х		Х			Х			Х			Х	Х	Х	Х
CCI	Х			Х		Х	Х			Х			Х			Х		Х	Х	Х
eGFR	Χ			Х		X	Х			Х			Χ			X		Χ	Х	Х
PK sample collection								See ta	able	below										
C3								See ta	able	below										
Complement pathway biomarkers in plasma ²¹								See ta	able	below										
CCI CCI						CCI														

										Т	reatn	nent	Period							
Period		Scree	ning																	
Visit Name	Screening	Rui	n-in	Base	eline		CCI			CC	Ί		– C0	CI			CC	CI	_	
Visit Numbers ¹	1	20		30	40	100	11	10		12	0		13	80		140	150	160	170	180
Days	-90 to -30	-89 to -40	-60 to -30	-30	-1	1	7	7		14	4		2	1		28	29	36	64	84
Time (post-dose)	-	-	-	-	-	Pre-dose	Pre-dose	0.5h	8h	Pre-dose	0.5h	8h	Pre-dose	0.5h 8	3h	Pre-dose	•	•	ı	-
Complement pathway biomarkers in serum ²³						See table below														
CCI				X		Х	Х			Х			Х			Х			X	х
Subject domiciled						Х									Х	•			Х	
Subject discharged						Х											Χ			
Adverse Events / Serious Adverse Events ²⁴									Х											
Concomitant medications / therapies									Х											
CCI _												Х	,							
Study completion information																				
Safety Follow up Call												·								

		Treatment Period				Sa	afety Follow-ı	up period	
Period			CO	CI					
Visit Name	CCI		CCI			Follow-up		EOS	Post study safety contact
Visit Numbers ¹	190	195	200	210	230	240	250	1999	
Days	85	169	92 or 176	99 or 183	113 or 197	127 or 211	155 or 239	183 or 267	Last treatment + 30 days
Time (post- dose)	-	-		-	-	-	-	-	-
Informed consent									
CCI									
Demography									
Inclusion / Exclusion criteria									
Medical history/current medical conditions									
Prior medications									
Physical Examination		S						S	
Hepatitis and HIV screen									

		Treatment Period				Sa	ıfety Follow-เ	p period	
Period			C	CI					
Visit Name	CCI		CCI			Follow-up		EOS	Post study safety contact
Visit Numbers ¹	190	195	200	210	230	240	250	1999	
Days	85	169	92 or 176	99 or 183	113 or 197	127 or 211	155 or 239	183 or 267	Last treatment + 30 days
Time (post- dose)	-	-		-	-	-	-	-	-

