- S Assessment to be recorded in the source documentation only
- Visit structure given for internal programming purpose only Commercially Confidential Information
- ³ Verify again the Inclusion Criteria #5,6,7, 11,12 and the Exclusion Criteria # 3, 5, 7, 8, 9, 10.
- Serum pregnancy test required at screening and at end of treatment. Urine pregnancy test at further time points.

- During treatment, assessment is performed pre morning dose
- ⁸ Renal biopsy has to be performed any time during screening period in case the most recent bioptic material is older than 12 months.
- ⁹ Includes pulse rate, blood pressure and temperature
- ¹⁰ Triplicate ECGs at all visits
- ¹¹ Including infection surveillance
- ¹² Including liver safety monitoring (ALT, AST, ALP, TBL, PT/INR, yGT levels assessment)
- 13 If not previously vaccinated, patients will receive vaccination against Neisseria meningitidis. Streptococcus pneumoniae, and Haemophilus influenzae according to local guidelines

Commercially Confidential Information

¹⁶ Includes UACR and UPCR, 24h urine excretion of albumin and protein, (PK only at Visit 140)

Commercially Confidential Information

19 During treatment, collection should be performed possibly at the same time, i.e. about half an hour after morning dose at site, except at Visit 180, where collection should be performed before starting the 24h urine collection, independently by the dose intake.

Commercially Confidential Information ²¹ Including, but not limited to, Factor Bb, and sC5b-9

Commercially Confidential Information

²⁴ All AEs will be collected from Informed Consent until the End Of Study visit, all SAEs will be collected until 30 days after the End Of Study visit

Commercially Confidential Information

- ²⁷ New dose capsules to be dispensed, see SOM for details
- ²⁸ To be performed pre-dose and 1h post dose

Commercially Confidential Information

³¹ It may be performed for screening purposes.

Table 8-2 Details for highly repetitive assessments, Cohort A

Table 8-3 Assessment Schedule, Cohort B

										7	reatr	nent	period							
Period		Scree	ning				CCI			CC	T		CC	~T			CC	ı		
Visit Name	Screening	Rui	n-in	Base	eline		CCI				71			J1				1		
Visit Numbers ¹	1	20		30	40	100	11	10		12	20		13	30		140	150	160	170	180
Days	-90 to -30	-89 to -40	-60 to -30	-30	-1	1	7	7		1	4		2	1		28	29	36	64	84
Time (post-dose)	-	-	-	-	-	Pre-dose	Pre-dose	0.5h	8h	Pre-dose	0.5h	8h	Pre-dose	0.5h	8h	Pre-dose	-	-	-	-
Informed consent	Х																			

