#### 1.3.2. Secondary objective(s)

Secondary objective(s)	Endpoint(s) related to secondary objective(s)	
• All Cohorts: To assess the relationship between LNP023 dose and pharmacodynamic biomarkers	Biomarker levels of blood Bb	
• All Cohorts: To assess the relationship between LNP023 dose and proteinuria	• 24h urine UPCR and UACR.	
All Cohorts: To assess the effect of LNP023 on renal function	
 
(i) change in and (ii) evolution of: urinary albumin (UA), urinary protein (UP) excretion; urine albumin to creatinine ratio (UACR) urine protein to creatinine ratio (UPCR), serum creatinine, estimated glomerular filtration rate (eGFR, using
 
	

	CKD-EPI formula), creatinine clearance, hematuria
• All Cohorts: To assess the effect of LNP023 on alternative complement pathway hyperactivity	• Blood level of C3.
• All Cohorts: To assess the safety and tolerability of LNP023	• ECG parameters, vital signs, safety laboratory assessments Commercially Confidential Information, AEs and SAEs.
• All Cohorts: To assess the plasma and urine pharmacokinetics of LNP023 in patients with C3G	
 
Plasma: Non-compartmental parameter analysis related to total drug, including but not limited to Cmax, Tmax, AUClast, AUCtau and Ctrough (Cmin) after the first dose on Day 7, Day 14, Day 21 and Day 28, as well as Cmin on Days 92 and 99 or 176 and 183.
 
Urine: Non-compartmental parameters, including but not limited to total cumulative urinary excretion (Ue) and renal plasma clearance (CLr).
 

• Cohort B: To evaluate the efficacy	• Ratio to baseline of UPCR and
of LNP023 in reducing proteinuria	UACR derived from 24h urine
at Week 12	collection.

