#### 6.1.3 Statistical model, assumptions and hypotheses

**Cohort A**: The log ratio to baseline in UPCR, will be analyzed using a mixed model repeated measures (MMRM), the analysis will include all data up to and including Week 12. This model will have the log ratio to baseline in UPCR as the dependent variable, baseline log transformed UPCR and time point (as study day relative to the start of study treatment, Day 28/29 and Day 84/85) as fixed effects. An unstructured covariance matrix will be used.

Model estimated means will be obtained at each timepoint, with Week 12 being of primary interest, along with the two-sided 80% confidence interval and p-value. Results will be back transformed to provide the geometric mean and their 80% CIs on the original scale.

Novartis	
SAP Addendum v02	

Model estimated means will be obtained at each timepoint, with Week 12 being of primary interest, along with the two-sided 80% confidence interval and p-value. Results will be back transformed to provide the geometric mean and their 80% CIs on the original scale.

**Cohort B**: The Wilcoxon signed rank test will be used for C3 Deposit Score data at Week 12 timepoint to compare the median difference of change from baseline between periods. The Hodges-Lehmann estimate and two-sided 80% confidence interval for the median difference will be provided.

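### The dose–proteinuria objective rests on 24-hour urine alone, which is never collected at the first three escalation dose levels

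*SAP*

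**What the plan says.** Protocol Table 2-1 sets, for all cohorts, the objective "To assess the relationship between LNP023 dose and proteinuria". The endpoint beside it, repeated in SAP 1.3.2, is "24h urine UPCR and UACR". SAP 6.2.1 defines the secondary proteinuria variables as "Raw and ratio to baseline in UA, UACR, UP and UPCR (all from 24h urine collection".

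Protocol 4.1 describes a four-week within-patient escalation and says "A PK assessment will be done on the last day of the respective dose level". The PK endpoint in Table 2-1 is set "after the first dose on Day 7, Day 14, Day 21 and Day 28".

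The model in SAP 6.1.3, which SAP 6.2.3 carries over in similar form to most secondary variables, has "time point (as study day relative to the start of study treatment, Day 28/29 and Day 84/85) as fixed effects".

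Tables 8-1 and 8-3 also carry a row "Spot urine collection - First Morning Void". Protocol 8.3.6 says these samples yield UPCR and UACR. Protocol section 3 and SAP 1.4 name both 24-hour and first-morning-void urine as ways of assessing proteinuria. SAP 6.2.1 does not list first-morning-void values.

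**The concern.** An objective about dose and proteinuria needs a proteinuria value at more than one dose. If the named endpoint is measured only at the end of escalation and at Week 12, it says nothing about the three lower levels. The study report would then list an objective that its own endpoint cannot address.

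The gap also conflicts with other commitments in the plan. Protocol 8.3 says pharmacodynamic samples are evaluated at all dose levels, and 8.3.5.1 counts UPCR and UACR among the pharmacodynamic renal parameters. SAP 6.1.2 promises plots of 24-hour UPCR over time by treatment level, which cannot be drawn for the first three levels.

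If first-morning-void values are brought in later to fill the gap, the choice would look post hoc.

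**Working it through.** The plan gives no figure to reproduce here. The check is one of visit coverage and does not involve sample size, power or alpha.

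**Inputs.** The ends of the dose levels come from the PK days (Table 2-1) read with protocol 4.1. Collection and dispensing days come from the columns of Tables 8-1 and 8-3, which agree between cohorts. New-dose dispensing is footnote 27 in Cohort A and footnote 28 in Cohort B: "New dose capsules to be dispensed, see SOM for details".

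| Day | Dose level ending | 24-hour urine | First morning void | New-dose capsules |
|---|---|---|---|---|
| 1 | none (baseline) | yes | no | first supply |
| 7 | 1 | no | yes, pre-dose | yes, at 8 h |
| 14 | 2 | no | yes, pre-dose | yes, at 8 h |
| 21 | 3 | no | yes, pre-dose | yes, at 8 h |
| 28 | 4 | yes | no | no |
| 36 | – | no | yes | no (resupply) |
| 64 | – | no | yes | no (resupply) |
| 84/85 | – | yes | no | not marked as new dose |

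Before treatment there is also an optional 24-hour collection at run-in, and first-morning-void samples at Visit 20 (run-in) and Visit 30 (Day -30).

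**Coverage by 24-hour urine.**
- Levels 1 to 3: 0 of 3.
- All four levels: 1 of 4, at Day 28.
- No new-dose dispensing is marked after Day 21 and up to Day 84, so Day 28 and Day 84 appear to share a dose. If the redacted table shows a change between them, 24-hour urine covers at most two dose levels, and still none of the first three.

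**Coverage by first morning void.** Levels 1 to 3: 3 of 3. Each sample is taken before the new capsules are dispensed that day, so it belongs to the level just completed. No sample is scheduled on Day 28, so neither method alone covers all four level-ends.

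**Values available for the gap**, assuming one value per patient per visit:
- Cohort A: 3 × 15 = 45 at planned enrolment; 3 × 12 = 36 at planned completers.
- Cohort B: 3 × 12 = 36 at planned enrolment; 3 × 10 = 30 at planned completers.

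Days 36 and 64 are later reference points and do not fill the gap.

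**The case against.** **Redaction.** The exploratory variables and analyses (SAP 6.3, protocol 12.6) are not visible, and first-morning-void proteinuria may already be summarised there. This stands as an unknown. It would not change the secondary endpoint, which is visible and limited to 24-hour urine.

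**Looser protocol wording.** The renal-function endpoint in Table 2-1 and the lists in protocol 12.5 and 12.5.1 do not tie UPCR to 24-hour urine throughout. Protocol 12.5.5 and SAP 8 plan plots of efficacy biomarkers against dose. However, the dose–proteinuria row itself names 24-hour urine, SAP 6.2.1 narrows the secondary variables to it, and neither plotting section says that proteinuria is included.

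**Role of first-morning-void urine.** Protocol 4.1 gives it to eligibility and easy monitoring, and names C3 and Bb as the key escalation biomarkers. That explains the omission. But protocol section 3 and SAP 1.4 also give it a role in assessing proteinuria, and the dose–proteinuria objective is still listed.

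**Limits of the remedy.** Dose and time rise together in every patient, spot samples are noisier than 24-hour collections, and the pre-treatment samples are early. All of this stands. The added data can describe the lower levels but cannot establish dose-response, which is why narrowing the objective is an acceptable alternative.

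**Cost.** Changing Table 2-1 needs a protocol amendment under section 14.1. That stands for the table, but the descriptive summary can be added in the SAP alone.

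**Conclusion.** The concern holds. As defined, the endpoint has no value at the first three escalation levels in either cohort and covers 1 of 4 levels on the visible schedule. It can compare baseline only with the later dose.

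The absence of 24-hour urine on Days 7, 14 and 21 is read directly from both schedules. Two points are inferences because the dose table is redacted: that there are four levels, and that Days 28 and 84 share one dose. The counts of 45 and 36 assume one value per patient per visit, since the footnotes on those cells are redacted.

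The consequence is limited to one secondary objective of a non-confirmatory study whose stated dose-finding basis is the complement biomarkers. Primary endpoints, sample size and power are unaffected. The change is worth making because the data are already being collected.

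**What to change.** In SAP 1.3.2 and 6.2.1, and in Table 2-1 if the protocol is amended, add first-morning-void UPCR and UACR at Days 7, 14 and 21 as descriptive data for this objective, with Days 36 and 64 as later reference points. Show them beside the 24-hour values without mixing the two, and specify the following:

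- **Baseline.** Define a separate first-morning-void baseline, for example the geometric mean of the available Visit 20 and Visit 30 samples. In Cohort A either sample can be the qualifying one (inclusion criterion 9), and both precede dosing by about a month or more. State that early falls may therefore partly be regression to the mean.
- **Within-treatment changes.** Show changes between Days 7, 14, 21, 36 and 64, which do not depend on that baseline.
- **Interpretation.** State that dose is confounded with time and cumulative exposure, that proteinuria may lag dose (the one-week steady-state argument in protocol 4.1 covers only C3 and Bb), and that no causal dose-response claim is made.

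Otherwise, narrow the objective to the dose levels that the 24-hour data cover. If the unpublished exploratory section already contains this summary, link it to the objective and check that it meets the points above.

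The cost is wording and one descriptive summary, plus an amendment if Table 2-1 is changed. No new sample, visit or patient is needed, and the 24-hour primary endpoint in Cohort A is unchanged.

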#### 6.2.2 Descriptive analyses

The following descriptive analyses will be implemented for each cohort separately and pooled cohorts.

The secondary variables, except hematuria, will be listed by treatment, subject and visit/time. Summary statistics will be provided by treatment and visit/time for raw, change from baseline and ratio to baseline as deemed relevant. Summary statistics will include mean (arithmetic and geometric), SD, CV, median, minimum, maximum. For parameters that will be analyzed as change from baseline, geometric means and CV will not be provided in the summaries.

Graphical methods will be employed to show group and individual summary plots over time by treatment. Individual plots for raw and change from baseline to week 12, will be plotted with median overlaid by treatment as well as arithmetic mean (SE) change from baseline to week 12

will be also plotted by Cohort for UPCR, UACR, eGFR, plasma Bb, serum C3 blood levels and C3 Deposit score.

A shift table of changes from baseline in hematuria levels will be provided, considering the following three levels:  $\langle 9rbc/hpf, \geq 9 rbc/hpf$  to  $\leq 50 rbc/hpf$  and  $\geq 50 rbc/hpf$  (where  $\geq 50 rbc/hpf$  cateogry includes also the too numerous to count (TNTC) values).

All Cohorts: Overlaying individual time profiles (spaghetti plots) to visualize trends in raw C3 deposit score by time and treatment group will be created.

